Official Title: **Weight management Aimed to Reduce Risk and Improve Outcomes from Radical Prostatectomy (WARRIOR)**

NCT Number: NCT03261271

Approval Date: March 23, 2020

**Weight management Aimed to Reduce Risk and Improve Outcomes from Radical
Prostatectomy
WARRIOR**

Principal Investigator: [name], RD, CSO
Department of Dietetics & Nutrition
Associate Professor
University of Kansas Medical Center
School of Health Professions
Department of Urology
[name] [name]
[contact] [contact]
e-mail: [contact]

Co-Investigators: [name], FACS
[name], RD

Study Coordinator: [name], RD
[name], Department of Urology

Statistician: [name]

Institutions: University of Kansas Cancer Center
[name]
[name]
[contact] [contact]

University of Kansas Medical Center
[name]
[name]

Funding:
[name] is supported by a Research Scholar Grant, RSG-17-050-01 - NEC, from the American Cancer Society. Project title: Weight Loss for Obesity-Driven Biomarkers of Prostate Cancer Progression

Protocol Version Date: March 23, 2020

Document Type: Amendment Protocol Version 3.0

Version Number: v4.0

CTRC Protocol #: 284

HSC #: STUDY00141060

PRMC approval date: 06/09/2017

Study name: **Weight management Aimed to Reduce Risk and Improve Outcomes from Radical Prostatectomy**

Nickname: **WARRIOR**

[figure not shown]
Protocol Synopsis

Title	Weight management Aimed to Reduce Risk and Improve Outcomes from Radical Prostatectomy WARRIOR
Nickname	
Primary Objective	To test the impact of weight management on obesity-driven prostate cancer biomarkers of recurrence and mortality taken at baseline, 1 week prior to surgery, and 6 months after surgery.
Secondary Objective	To evaluate how weight management affects weight loss, body composition, and weight maintenance in overweight and obese men with localized prostate cancer.
Sample Size	40
Summary of Subject	Men undergoing a prostatectomy
Eligibility Criteria	
▪ Minimum age of 50▪ BMI 25-45 kg/m²▪ Minimum 4 weeks lag-time until prostatectomy▪ Internet access▪ iDevice* (iPad, iPod, iPad mini, iPhone) *iDevices may be issued by the research team to be returned at the end of the study.
Procedures	Participants will undergo a pre-surgical weight loss intervention prior to scheduled prostatectomy and a 6-month post-surgical weight maintenance program after prostatectomy.

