Immune suppressive factors lead to PCa recurrence and death. Myeloid-derived suppressor cells (MDSCs) play a crucial role in cancer-induced immune dysfunction by establishing an immune suppressive environment in prostate tumors.⁴ High levels of MDSCs are associated with a shorter survival in PCa patients.⁵ Furthermore, MDSC frequencies correlate with PCa stage.⁶ Prostate tumors express high concentrations of pro-inflammatory cytokines and MDSCs,⁵ which lead to immunosuppression thereby making it more difficult for the immune system to keep cancer in check.⁷ Interestingly, the monocytic MDSC subtype is predominant in the blood of patients prior to RP when the tumor is present, but the frequency of the monocytic MDSC subtype decreases after the tumor is removed.⁸ Furthermore, our team routinely measures MDSCs in patients before and after cancer surgery.⁹ Our pilot data show reduced total and monocytic MDSCs in the weight management intervention ($P = 0.09$; $P = 0.17$, respectively), and the changes in these cell frequencies were different compared to the prospective controls before RP ($P = 0.06$; $P = 0.17$, respectively). We also found that the monocytic MDSC frequencies decrease substantially after RP, but total MDSCs and Tregs do not change with the removal of the tumor. These observations support that the intervention timing is ideal to evaluate the effects of weight loss on tumor-mediated immunosuppressive mechanisms in the peri-operative time frame.

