maintenance after PCa surgery on obesity-driven PCa biomarkers. Forty men with stage T1 or T2 PCa scheduled to undergo RP will be randomized to receive a weight management program (intervention; n = 20) or standardized education materials (control; n = 20). Our pilot work has established that men awaiting RP are very motivated and embrace the pre-surgical intervention as a means to cope with anxiety by improving their health. We employ a weight loss intervention that emphasizes competition, autonomy, technology, cost savings, and male-specific barriers to change—factors that prior studies have found to be important to successful weight loss interventions among men. We also examine critical QoL factors that could affect the feasibility of the intervention in future trials and clinical practice. Our hypotheses and specific aims are:

1. *To test the impact of weight management on obesity-driven PCa biomarkers taken at baseline, 1 week prior to surgery, surgery and 6 months after surgery.

Hypothesis 1.1: Immune suppressive factors will respond to the intervention with reduced total MDSC (Lin- CD11b+ CD33+) and monocytic MDSC (Lin- CD11b+ CD33+ CD14+ CD15-) counts compared to baseline values and to the control group. **Primary Objective**

Hypothesis 1.2: Participants in the intervention group will have a more favorable chemokine, adipokine, and cytokine profile than the participants in the control group.

2. To evaluate how weight management affects weight loss, body composition, and weight maintenance in overweight and obese men with localized PCa.

Hypothesis 2.1: The intervention will lead to significant weight reduction compared to the control group from baseline to 1 week prior to surgery.

Hypothesis 2.2: The intervention will reduce body fat and maintain lean body mass as measured by Dual Energy X-Ray Absorptiometry (iDXA) scans from baseline to 1 week prior to surgery.

Hypothesis 2.3: The intervention will lead to weight maintenance (<3% regain) 6 months after RP.

3. To test the impact of weight management on QoL in PCa survivors.

Hypothesis 3.1: The intervention will report better urinary function and lower urinary bother compared to control 6 months after RP as measured by the Expanded PCa Index Composite (EPIC) Instrument-26.

Hypothesis 3.2: The intervention will improve sexual function and QoL 6 months after RP as measured by the EPIC-26.

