4. To test the impact of weight management on gut microbiome composition at baseline, prior to surgery and 6 months after surgery.

[figure not shown]
Hypothesis 4.1: The intervention will provide the knowledge of dominant microbial populations before and after weight management.

Hypothesis 4.2: The intervention will also identify the microbial populations that are altered by surgery.

Impact. Weight loss prior to RP may offer a low risk, high-impact means of protecting against PCa progression. Data suggest that weight loss decreases inflammation and improves insulin sensitivity, but the effect of weight loss on the specific immune cell types known to mediate PCa progression is completely unknown. Filling this gap is critically important since these immune cells are the primary drivers of the inflammation that influences PCa progression. Our multidisciplinary research team is uniquely qualified to successfully conduct the proposed study. This project will determine whether weight loss can alter obesity-driven PCa biomarkers and will lay the groundwork for a definitive multi-site trial to test the effects of weight loss and biomarker changes on PCa recurrence, QoL, and survival.

RESEARCH DESIGN AND METHODS

AIM 1: Test the impact of weight management on obesity-driven PCa biomarkers taken at baseline, 1 week prior to surgery, and 6 months after surgery.

We aim to assess the effect of a novel weight loss intervention before and weight maintenance intervention after PCa surgery on obesity-driven PCa biomarkers. We will measure obesity-driven PCa biomarkers, body weight, body composition, and urinary/sexual QoL at baseline, 1 week prior to RP, and 6 months after PCa surgery (See **Table 3: Schedule of Evaluations**). We will test the proposed objectives in a randomized, clinical trial providing either a weight management program (intervention group; n = 20) or standardized educational materials (control group; n = 20) to forty men with stage T1 or T2 PCa planning to undergo RP (See **Figure 2: Schema, Experimental Details**). We will use permuted block randomization.

Patients will be assigned to one of the two treatment groups using a randomization list created by the statistician. The randomization scheme will assure that the groups are balanced at every block of 10.

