Sample collection, processing, and analysis. Whole blood and fecal samples will be collected at baseline, 1 week prior to surgery, and 6 months post-operation. Fresh prostate tissue will be collected and flash-frozen from the RP and stored in vapor phase nitrogen. Paraffin-embedded prostate tissue will also be collected from the RP. Since the majority of PCas originate in the peripheral zone, we will obtain samples from 4 quadrants of the prostate peripheral zone in normal/tumor pairs. H&E staining will determine malignant versus benign tissue. Periprostatic adipose tissue will be collected from the RP.

Blood Immune biomarkers. The primary objective of this project is to assess the impact of weight loss before and weight maintenance after PCa surgery on immunosuppressive factors compared to a randomized control. Although our pilot data suggest MDSCs are a logical target for obesity-driven PCa progression, our team is aware of how other immune cells play an interconnected role. We carefully chose biomarkers that fit our hypothesis within the budget constraints, we will analyze MDSCs and their subtypes, Natural Killer (NK) Cells, and regulatory T cells (Tregs). MDSC subpopulations are defined according to published methods⁷³ of grouping granulocytic (Lin⁻ CD11b⁺ CD33⁺ CD14⁻ CD15⁺), monocytic (Lin⁻ CD11b⁺ CD33⁺ CD14⁺ CD15⁻), and immature (Lin⁻ CD11b⁺ CD33⁺ CD14⁻ CD15⁻). Natural Killer (NK) cells are defined by CD56 and CD16 expression, and regulatory T cells (Tregs) by CD4+, CD25+, FoxP3+ expression in the blood. Please see our recent publication⁹ for additional information about our method.

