Immune Biomarkers		X	X	X
Inflammation Biomarkers		X	X	X
Cardiometabolic Markers		X	X	X
Microbiome		X	X	X

Justification of sample size: We powered this study for aims 1 and 2, but aim 3 and 4 are exploratory. The power calculations used effect sizes and standard deviations from our pilot study (ClinicalTrials.gov: NCT02252484). The primary objective is to reduce obesity-driven biomarkers (MDSCs) of PCa recurrence and death. Our pilot study showed that weight loss of 1.2 pounds/week corresponds to a decrease in MDSC by 1.4 counts/week. Group sample sizes of 17 and 17 achieve over 80% power to detect a change in MDSC of 1.2 per week between the intervention and control groups with standard deviations of 1.6 and 0.3 (obtained from our pilot study) with a significance level of 0.05 using a two-sided, two-sample t-test. Secondary objective: Thirty-four participants will detect weight change as low as 0.5 kg/week between the intervention and control groups using the standard deviations of 0.6 and 0.1, from our pilot study. Weight maintenance will also be examined. If the intervention maintains their weight loss within 3%, 17 patients will give power over 80% to detect equivalency in the intervention group assuming the moderate correlation of 0.4 using paired t-tests. Tertiary objectives to assess the impact of weight loss on QoL using the EPIC-26 tool are exploratory. The results will be used to calculate effect sizes for a definitive, large multi-site clinical trial.

Statistical Analysis Prior to initiating outcome analyses, we will summarize the baseline characteristics of the data. Tests will be considered significant if the *P*-value is less than 0.045 for the final analysis. Our data may include missing observations related to either attrition or nonresponse and this type of missing data can reasonably be assumed to be random. We will run an intention to treat analysis for all outcomes. Comparisons will be carried out separately for the weight loss phase (enrollment to 1 week prior to surgery) and the weight maintenance phase (1 week prior to surgery to 6 months after surgery). Since patients will be on the pre-surgical phase for varying durations of time, we will assess the rate of weight loss between the two groups. A two-sample t-test will be used to assess the differences in outcomes between the two groups. The significance of within-group differences will be assessed using a paired t-test.

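### The plan specifies no between-arm 6-month biomarker comparison referenced to, or adjusted for, the enrollment value; its second comparison window starts after randomized treatment has begun

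*Combined protocol and SAP*

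**What the plan says.** The Statistical Analysis section is the only analysis text for these outcomes; the Synopsis repeats just its two t-test sentences. It analyses two phases separately. The first runs from enrollment to the visit one week before surgery. The second is described as "and the weight maintenance phase (1 week prior to surgery to 6 months after surgery"). For the arm comparison it says "A two-sample t-test will be used to assess the differences in outcomes between the two groups", and within-arm differences get a paired t-test. It names no covariate, no longitudinal model and no enrollment-to-6-month window, and it does not say whether the 6-month outcome is a change or a level.

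The objectives reach further:

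- Synopsis, Primary Objective: "obesity-driven prostate cancer biomarkers of recurrence and mortality taken at baseline, 1 week prior to surgery, and 6 months after surgery".
- Research Design and Methods, Aim 1: the effect of a "weight loss intervention before and weight maintenance intervention after PCa surgery on obesity-driven PCa biomarkers".
- Blood Immune biomarkers: the primary objective includes "weight maintenance after PCa surgery on immunosuppressive factors compared to a randomized control".
- Hypothesis 1.1, marked as the primary objective: reduced MDSC "counts compared to baseline values and to the control group". It names both references but gives no visit and no test.

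Hypothesis 3.1 is worded as a 6-month level ("better urinary function and lower urinary bother compared to control 6 months after RP"), but it concerns EPIC-26 only. Under Research Design and Methods, the randomized program runs for 4-16 weeks before surgery, so the visit that opens the second window comes after randomized treatment.

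**The concern.** A comparison that starts at a post-randomization visit subtracts whatever the intervention has already achieved. If the program lowers MDSCs before surgery and the reduction lasts, the two arms change alike from then on, and a test of that change finds nothing. If part of the reduction is lost, the intervention arm rises relative to control and the test points against it, even though that arm is still better off at 6 months.

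At stake is the 6-month part of the primary objective, for MDSCs and for the Hypothesis 1.2 markers. The same data could be reported as a lasting benefit, as no difference or as a reversal, depending on which of two unstated readings the analyst adopts.

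**Working it through.** **The plan's own figures.** Inputs from the sample size section: 17 per arm, difference 1.2 per week, SDs 1.6 and 0.3, two-sided alpha 0.05. The root-mean-square SD is √((1.6² + 0.3²)/2) = 1.151. Power is 83.8% (pooled t, 32 df) or 81.7% (Welch, 17.1 df); at the final alpha of 0.045 it is 82.6% or 80.3%. The claim of over 80% is reproduced. Enrollment also reproduces: 34/0.9 = 38 and 38/0.95 = 40. These figures concern a per-week difference; no power is stated for a 6-month biomarker contrast.

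**Change reading.** Let e1 and e2 be the intervention-minus-control differences before surgery and at 6 months (negative = benefit). The second-phase contrast has expectation e2 − e1. A surgical fall common to both arms cancels. With a fraction r of e1 retained, e2 = r·e1, so the contrast is −(1 − r)·e1. For an assumed e1 = −1 SD:

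| r | True 6-month effect | Second-phase contrast |
|---|---|---|
| 1 | −1.00 | 0 |
| 0.75 | −0.75 | +0.25 |
| 0.5 | −0.50 | +0.50 |
| 0 | 0 | +1.00 |

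To see how often this would be significant, assume equal visit SDs of 1, visit correlation ρ, 17 per arm and alpha 0.045. The change then has SD √(2(1 − ρ)), or 1.265, 1.095, 0.894 and 0.632 at ρ = 0.2, 0.4, 0.6 and 0.8. By the noncentral t with 32 df, a +0.50 contrast (r = 0.5) is significant in 19%, 24%, 34% and 59% of trials.

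At r = 1 the rejection rate is alpha, 4.5%; simulation with a common post-surgical fall of 1.5 SD gave 4.3-4.7%. That needs similar SDs in the two arms. With SDs in the ratio 1.6 to 0.3, a pooled t-test rejects in about 5.2%; Welch keeps 4.5%.

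**Level reading.** The expectation is e2, so there is no bias. Against ANCOVA on the enrollment value, the large-sample variance ratio is 1/(1 − ρ²). At 17 per arm, ANCOVA also pays for chance imbalance in the covariate, a factor of about 1 + 1/30 (32 within-arm df, less 2):

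| ρ | Large sample | 17 per arm |
|---|---|---|
| 0.2 | 1.04 | 1.042/1.033 = 1.01 |
| 0.4 | 1.19 | 1.190/1.033 = 1.15 |
| 0.6 | 1.56 | 1.562/1.033 = 1.51 |
| 0.8 | 2.78 | 2.778/1.033 = 2.69 |

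Illustrative power at alpha 0.045 for true 6-month effects of 0.6, 0.8, 1.0 and 1.2 SD:

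- Level t-test: 38, 60, 79 and 92%.
- ANCOVA (simulated), ρ = 0.2: 38, 61, 79 and 92%.
- ANCOVA (simulated), ρ = 0.4: 43, 66, 85 and 95%.
- ANCOVA (simulated), ρ = 0.6: 53, 78, 93 and 98%.

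**The case against.** The strongest reply is that the second window is labelled a maintenance phase. For maintenance, a contrast near zero after a first-phase benefit is the hoped-for result, and the first-phase result stands beside it. In change units, and in the same patients, the two contrasts add up to the enrollment-to-6-month contrast. This has force: a reader who takes both phases together would not be misled, and the window suits the under-3% regain question in Hypothesis 2.3. But the sum has no prespecified test, and it is not direct if the first phase is reported as a weekly rate, the scale on which the MDSC power is stated.

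A second reply is that Hypothesis 1.1 already names baseline and control. It does, but without a visit or a test it does not choose between the readings. A third is that 6-month levels may be intended, as in Hypothesis 3.1. That is possible, and then only precision is lost.

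The support for full retention is also thin. The Background reports from the pilot that "the monocytic MDSC frequencies decrease substantially after RP, but total MDSCs and Tregs do not change with the removal of the tumor", and elsewhere suggests that the total MDSC reduction held during maintenance. Neither statement documents a stable control arm over six months. The identity e2 − e1 does not depend on this, but how likely full retention is does.

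**Conclusion.** The concern holds as a gap in specification. The 6-month part of the primary objective has no stated between-arm comparison referenced to, or adjusted for, enrollment. On the natural reading, the comparison that is stated answers whether the arms diverge after surgery, and not whether the randomized arms differ at 6 months. Under that reading the distortion is (1 − r) times the pre-surgery effect, against the intervention. Under the level reading the loss is negligible at a visit correlation of 0.2 and large at 0.6 or above.

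Four stronger conclusions that a reader might infer are not supported:

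- That the second phase has no estimand. It has one, the difference in maintenance-phase change, but it is not the 6-month effect.
- That the 6-month analysis is necessarily biased. The text permits an unbiased level comparison.
- That the second-phase test at full retention rejects at exactly alpha under any SDs. With a pooled test and very unequal SDs it is slightly above.
- That the sample size or power is wrong. Both reproduce, and the pre-surgery comparison is untouched.

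Effect sizes, retention fractions and biomarker visit correlations are assumptions; the plan gives a correlation (0.4) only for the weight-maintenance test. This should be fixed; confidence is medium because the text leaves the reading open.

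**What to change.** In the Statistical Analysis section, add that the between-arm 6-month analysis of the Aim 1 biomarkers (MDSCs and the Hypothesis 1.2 markers) is the 6-month difference adjusted for the enrollment value, by ANCOVA or by one longitudinal model using all three visits. Keep the pre-surgery-to-6-month change as the maintenance-phase analysis, including the under-3% regain question, and state that it is not the estimate of the 6-month treatment effect.

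The cost is one or two sentences. Blood biomarkers are already scheduled at all three visits in both arms, so no patients, visits or assays are added.

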Therefore, 34 eligible, randomized patients will provide sufficient power for both aims 1 and 2. However, based on our pilot study, we anticipate that 10% of patients will drop out by the 6 months follow up. Incorporation of this dropout rate inflates the required sample size by a

factor of $34/0.9 = 38$ eligible patients. Finally, assuming a 5% ineligibility rate, a total of $n = 40$ registered patients will be required. A single interim analysis for efficacy will be conducted when 50% of patients achieve their endpoint, at the alpha = 0.005 level. Accordingly, the final analysis will be conducted at the alpha = 0.045 level.

Potential difficulties

- *Tracking/technology.* In our pilot study, many participants were unfamiliar with the technology used and they had never tracked diet or physical activity before. For these participants, we initially offered paper journals so they could track their meal plans by hand. Then, coaches would help them enter the data at the visits. We will offer the same strategy in this project. Also, some participants wanted to remove their accelerometers after surgery because their step counts dropped so low. Our team affirmed that disruptions in sedentary activity (as prompted by the Vivofit® 3) is more important for their health than absolute step counts in the early days after surgery. Coaching participants to reframe negative feelings has helped to overcome this obstacle.

PROTECTION OF HUMAN SUBJECTS

Recruitment Potential subjects will be approached by their urologist or oncologist and informed about the possibility of research participation. Patients who are interested in learning more about participation will be introduced to the study coordinator who will then explain the study in detail. The potential subjects will have the opportunity to read the consent form in the absence of the PI and study team. It will be explained to the subjects that the study is voluntary and that they may discontinue at any time without prejudice.

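### The MDSC comparison is an unadjusted t-test although baseline MDSC is measured in everyone; baseline adjustment is a cheap precision gain, not the repair of an error

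*Combined protocol and SAP*

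**What the plan says.** Hypothesis 1.1, marked as the primary objective, expects lower total and monocytic MDSC "counts compared to baseline values and to the control group". Under Sample collection, processing, and analysis, and in the Immune Biomarkers row of Table 3, blood is taken from all participants at baseline, one week before surgery and six months after it.

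The Justification of sample size uses 17 per group "to detect a change in MDSC of 1.2 per week between the intervention and control groups", with pilot SDs of 1.6 and 0.3, a two-sided alpha of 0.05 and a two-sample t-test, and claims over 80% power.

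Statistical Analysis then applies one sentence to every outcome: "A two-sample t-test will be used to assess the differences in outcomes between the two groups". The Synopsis repeats it. The weight-loss and maintenance phases are compared separately. Because the pre-surgical period varies in length, "we will assess the rate of weight loss between the two groups"; that paragraph does not mention a rate for MDSC. Neither section names a baseline covariate, ANCOVA or a mixed model.

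On timing: "A single interim analysis for efficacy will be conducted when 50% of patients achieve their endpoint", at alpha 0.005, with 0.045 left for the final analysis.

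**The concern.** A baseline measurement of the primary outcome is often its best available predictor, and here it costs nothing extra. A t-test on change subtracts the baseline with a fixed coefficient of 1. ANCOVA estimates the coefficient, and so removes the part of the change that the starting level explains. With 17 per arm and power just above 80% at the final alpha, there is little room for extra variability or dropout. A few points of power from data already in hand are worth having. The choice of covariate should be written down before anyone sees outcome data, which the interim look brings forward.

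**Working it through.** **Inputs.** From the documents: n = 17 per arm, difference 1.2 per week, SDs 1.6 and 0.3, two-sided alpha 0.05 for planning and 0.045 for the final analysis. Assumed: r, the size of the correlation between weekly change in the intervention arm and baseline MDSC. The documents do not give it.

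**Step 1: the plan's own figure.** SE = √[(1.6² + 0.3²)/17] = √(2.65/17) = 0.395. Noncentrality = 1.2/0.395 = 3.04. Degrees of freedom are 32 (pooled) or, by Satterthwaite, 2.65² × 16/(1.6⁴ + 0.3⁴) = 17.1 (Welch). Noncentral t power:

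| alpha | pooled | Welch |
|---|---|---|
| 0.05 | 83.8% | 81.7% |
| 0.045 | 82.6% | 80.3% |

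The claim of over 80% reproduces.

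**Step 2: what adjustment can gain.** Model: weekly change on arm and baseline, one common slope. Suppose change is correlated r with baseline in the intervention arm and uncorrelated in the control arm. Per SD of baseline, the slopes are 1.6r and 0, and the fitted common slope is about 0.8r. The residual variances are then
- intervention: 2.56(1 − r²) + 0.64r² = 2.56 − 1.92r²
- control: 0.09 + 0.64r²

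They sum to 2.65 − 1.28r², so the large-sample variance ratio against the t-test is 1 − 1.28r²/2.65. This is 0.88 at r = 0.5 and 0.76 at r = 0.7. Estimating the slope costs about 3% at this sample size (simulated ratio 1.03 at r = 0). The simulated ratios are therefore 0.91 and 0.80, worth about 10% and a quarter more participants.

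**Step 3: simulated power, 17 per arm, alpha 0.045, 100,000 trials per row.**

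| r | t, pooled | t, Welch | ANCOVA, model-based | ANCOVA, HC3 |
|---|---|---|---|---|
| 0 | 82.5 | 80.5 | 81.2 | 78.3 |
| 0.3 | 82.4 | 80.4 | 82.7 | 79.7 |
| 0.35 | 82.1 | 80.1 | 83.1 | 80.2 |
| 0.4 | 82.2 | 80.1 | 84.0 | 81.0 |
| 0.5 | 82.4 | 80.5 | 85.9 | 82.8 |
| 0.7 | 82.5 | 80.5 | 90.5 | 87.3 |

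Model-based ANCOVA overtakes the pooled t-test at about r = 0.25. HC3 overtakes Welch near 0.35 and the pooled t-test near 0.5.

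**Step 4: type I error at nominal 0.045.** Pooled t is slightly high, about 0.051 to 0.054. Model-based ANCOVA is similar, about 0.050 to 0.053. Welch is about 0.044 to 0.046. HC3 is slightly conservative, about 0.038 to 0.044.

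**Step 5: what r might be (illustration only).** With equal SDs at the two visits, a constant duration and a baseline to pre-surgery correlation ρ, r = √[(1 − ρ)/2] in size. For ρ = 0.4, 0.6, 0.8 and 0.9 this gives 0.55, 0.45, 0.32 and 0.22. The HC3 break-even of 0.35 against Welch corresponds to ρ of about 0.75.

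**The case against.** The strongest reply is that nothing here is wrong. In a randomized trial the t-test is valid, it is the test the study was powered on, and its power reproduces. That stands in full. A reader might infer from the word unadjusted that the plan ignores baseline. The documents do not support that: power is set on change per week, and Hypothesis 1.1 compares with baseline, so baseline already enters by subtraction.

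A reader might also infer that the MDSC scale is undefined. It is given in the sample-size paragraph directly before the analysis paragraph. Repeating it is a clarification only. Nor is the weekly rate always the most powerful scale. If durations are assumed uniform over 4 to 16 weeks, total change gives anywhere from 78%/75% (pooled/Welch) to 93%/92%, depending on how the noise behaves. The rate is kept because the study was powered on it.

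The gain can also be overstated. Multiplying the variance of change by (1 + ρ)/2 in both arms gives, for example, 92.0% at ρ = 0.4 (Welch-type degrees of freedom). But randomized arms share a baseline SD, and one common slope cannot remove the same share of variance from arms with SDs of 1.6 and 0.3. The table in the working is the safer guide.

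Finally, the price of HC3 depends on the comparator. At r = 0 it loses about 2 points against Welch but about 4 against the pooled test, and the plan does not say which t-test it means. Dividing by a varying duration also weakens r: a correlation of 0.45 with total change becomes about 0.39 to 0.42 on the rate. With constant visit noise, HC3 then gives 81.8%, against 80.7% for Welch and 82.4% for pooled. This stands. The gain is real only if change depends appreciably on baseline.

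**Conclusion.** The point holds as a precision improvement, not as an error in the test or the power calculation. Baseline MDSC is available in every participant and the planned comparison does not use it as a covariate. At 17 per arm and alpha 0.045, adjustment changes power from 82% (pooled) or 80% (Welch) to about 81%, 86% or 90% model-based, and 78%, 83% or 87% with HC3, at r = 0, 0.5 and 0.7. These figures assume normal outcomes, a linear relation with baseline, and control-arm change unrelated to baseline. If both arms correlate with baseline at 0.5 or 0.7, power is higher: 88% (HC3 85%) or 93% (HC3 91%).

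The one correlation in the documents, 0.4, belongs to the weight-maintenance calculation and cannot stand in for MDSC. The size of the gain therefore stays an assumption.

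**What to change.** In Statistical Analysis, before the interim analysis, replace the MDSC t-test with ANCOVA of weekly change over the weight-loss phase on arm and baseline MDSC, for the counts named in Hypothesis 1.1. Use heteroscedasticity-robust (HC3) standard errors, because the stated SDs are 1.6 and 0.3. For the maintenance phase, adjust for the enrollment value; the pre-surgery value comes after randomization and is itself affected by arm. Adjusting other outcomes for their own baseline is optional and does not carry this point.

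The cost is wording only, with no extra visits, samples or participants. Statistically it uses one degree of freedom and assumes linearity. If r is near zero, model-based ANCOVA loses about 1 point against the pooled t-test, and HC3 loses about 2 against Welch and 4 against pooled.
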